8.3.2 Analysis of Secondary Endpoints

- Revision of any component for any reason – Revision will be evaluated as the frequency of subjects with component revision at the end of study and expressed as a percentage of the full analysis set.
- Standard of Care Radiographic assessments
 - Loosening as indicated by radiolucencies > 2mm - a binary variable will be used to categorize subjects with radiolucencies > 2mm or below at all recorded time points. The frequencies together with percentages will be reported. The results will be further categorized as subjects with pain, swelling and functional limitations.
 - Evidence of surface wear or particulate debris generation as indicated by early osteolysis, implant migration, or other clinical or radiographic abnormalities such as pseudo tumors or corrosion

The presence of surface wear and all types radiographic abnormalities will be summarized as frequencies together with percentages at all recorded time points.

- HOOS JR Questionnaire
 - The score will be calculated to assess clinical efficacy

The HOOS score will be summarized using mean, median, SD, minimum and maximum at all recorded time points for all subjects. The results will be further categorized as subjects with pain, swelling and functional limitations. An exploratory t-test will be fitted to evaluate the difference between baseline and end of study scores.

- Device Related Adverse Events
 - Safety will be evaluated by assessing the frequency and nature of Device related adverse events as defined in the Safety Reporting section

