5.5.1 Baseline Visit

- Informed Consent
- Implant and Joint Status
- Operative Date
- Demographics
- Medical History and Concomitant Medication
- HOOS JR Questionnaire
- Radiographic evaluation
- Adverse events assessment
- Metal Ion Level assessment
 - Whole blood will be collected for metal ion testing of cobalt and chromium
- MARS MRI/CT
 - Subjects with whole blood metal ion levels > 7 ppb will have a MARS MRI performed (or CT if the MRI is contraindicated)
- Study termination, if applicable

5.5.2 1 Year/3 Year Visits (\pm 3M) up to 20 years post implant Follow Up

Annual visit schedule for symptomatic subjects and 3 Year visit schedule for non-symptomatic subjects

- Implant Status

- Demographics
- Medical History and Concomitant Medication
- HOOS JR Questionnaire
- Radiographic evaluation
- Adverse events assessment
- Metal Ion Level assessment
 - Whole blood will be collected for metal ion testing of cobalt and chromium
- MARS MRI/CT
 - Subjects with metal ion levels > 7 ppb will have a MARS MRI performed (or CT if MRI is contraindicated)
- Study termination, if applicable

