8.1 Analysis Population

Intent-to-Treat (ITT) Population

The ITT population includes all subjects who met the inclusion criteria and are sequentially enrolled to the study based on medical record review and confirmation of Short Modular Femoral Stem implant surgery for a THA arthroplasty prior to IRB/EC approval of this protocol.

Per Protocol (PP) Population

The Per-protocol population (PP) population includes all enrolled subjects who received the assigned treatment and do not have major protocol violations. The PP population will be established after a review of protocol deviations. All efficacy analyses will be performed on the PP population.

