8.2 Statistical Design

A Statistical Analysis Plan (SAP) will be written and finalized prior to database lock. The following is a brief description of the analyses to be described in this plan. The SAP will be more detailed and account for all analyses.

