8.3 Efficacy Analysis

The primary objective of this study is to provide safety data for the SMF Short Modular Femoral Stem Hip System up to a follow up period of 20 years post implant. The indicators of efficacy of hip arthroplasty with the SMF Short modular femoral stem will be evaluated through the analysis of primary and secondary endpoints. For all continuous endpoints, 95% confidence intervals (CI) for the means will be reported.

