8.5 Missing Data

A complete accountability report, along with the explanation for lost-to-follow-up, death, revision, and withdrawn subjects, will be provided in the Clinical Study Report (CSR). A complete list of the informative/non-informative missing data will be also be provided in the CSR. Due to the nature of the study, no imputation of missing data is planned.

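### Revision is planned as a crude percentage of an undefined analysis set with no rule for losses; with all enrolled as denominator it understates revision risk, by a modest amount

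*Combined protocol and SAP*

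**What the plan says.** Section 8.3.2 defines the revision result as the "frequency of subjects with component revision at the end of study and expressed as a percentage of the full analysis set". This is the only use of the term *full analysis set*. Section 8.1 defines two populations. For the first it says: "The ITT population includes all subjects who met the inclusion criteria and are sequentially enrolled to the study". The second, PP, removes subjects with major protocol violations, and the section adds: "All efficacy analyses will be performed on the PP population". Revision sits under section 8.3, headed Efficacy Analysis, which states that efficacy "will be evaluated through the analysis of primary and secondary endpoints".

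On losses, section 8.5 promises an accountability report covering loss, death, revision and withdrawal, together with "A complete list of the informative/non-informative missing data". It then says: "Due to the nature of the study, no imputation of missing data is planned". No censoring rule or time-to-event method appears anywhere. Section 8.2 describes section 8 as a brief outline and says: "The SAP will be more detailed and account for all analyses". That separate SAP is not among the documents.

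Subjects enter about 8 to 9 years after implantation with the original implant in place (synopsis; section 5.3) and are followed to 20 years. Section 5.5.2 sets the "Annual visit schedule for symptomatic subjects and 3 Year visit schedule for non-symptomatic subjects".

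**The concern.** Two things are open: who is in the denominator, and what happens to a subject whose follow-up stops early. If the denominator is everyone enrolled, a subject lost in year 3 stays in it as a non-event to the end of the study, although a later revision would not be seen. Non-symptomatic subjects are seen only every 3 years, so implant status may be unknown for some time before a loss is noticed.

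The direction matters. Section 1.0 gives possible greater revision risk as the reason for the field action. On the natural reading, the error from losses makes the device look safer, and the 95% confidence interval planned in section 8.2.1 does not allow for it.

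A smaller inconsistency: the synopsis counts revision of components of the study device, while sections 3.2 and 8.3.2 count any component.

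**Working it through.** The plan has no figure to reproduce. The sample size of up to 26 is based on feasibility, and no revision, loss or death rate is stated. The rates below are assumptions.

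**Follow-up.** 20 − 9 = 11 and 20 − 8 = 12 years on study. Allowing for the 6-month window at the end-of-study visit, the shortest planned span is 20 − 9 − 0.5 = 10.5 years. A 10-year time point after baseline is therefore supported, entry being approximate.

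**Formulas.** Constant hazards: r for revision, w for loss or withdrawal, h = r + w, horizon T.
- True risk = 1 − exp(−rT)
- Crude percentage, all enrolled = (r/h)(1 − exp(−hT))

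**Results at T = 10, r = 0.02.** True risk = 1 − exp(−0.2) = 18.13%.

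| Loss per year | Crude percentage | Shortfall × 26 |
|---|---|---|
| 0.5% | 0.8 × (1 − exp(−0.25)) = 17.70% | 0.11 |
| 1% | 0.667 × (1 − exp(−0.3)) = 17.28% | 0.22 |
| 2% | 0.5 × (1 − exp(−0.4)) = 16.48% | 0.43 |
| 4% | 0.333 × (1 − exp(−0.6)) = 15.04% | 0.80 |
| 6% | 0.25 × (1 − exp(−0.8)) = 13.77% | 1.13 |

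With revision at 1 to 3% a year and the same loss rates, the shortfall runs from 0.06 to 1.60 subjects at 10 years and from 0.08 to 2.00 at 11.5 years.

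**Against sampling error.** The standard error of a proportion of 18.1% in 26 subjects is √(0.181 × 0.819/26) = 7.6 percentage points. The largest shortfall in the table is 18.13 − 13.77 = 4.4 points.

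**Other denominator.** If PP applied and every lost subject were dropped, the figure would be crude/(crude + exp(−hT)). At 10 years this is 17.70/(17.70 + 77.88) = 18.5% at 0.5% loss and 13.77/(13.77 + 44.93) = 23.5% at 6% loss. The error reverses direction.

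**Death.** Adding death at d = 0.02 a year, the 10-year cumulative incidence of revision is 0.5 × (1 − exp(−0.4)) = 16.5%. With no loss, the crude percentage estimates exactly this, so deaths kept in the denominator do not cause the understatement. With loss at 2 to 6% a year, the crude figure falls to 15.0 to 12.6%.

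**Count example (invented).** Of 26 enrolled, 3 are revised (years 2, 5, 9) and 6 lost (years 1, 3, 4, 6, 7, 8). Crude: 3/26 = 11.5%, exact 95% CI 2.4 to 30.2%. With losses censored, 25, 22 and 18 are at risk at the three revisions, so the estimate is 1 − (24/25)(21/22)(17/18) = 13.5%, log-log 95% CI 4.5 to 36.4%.

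**The case against.** The best defence is that the plan promises only a descriptive frequency. Revision is a secondary endpoint, all tests are exploratory, and no comparator or decision rule rests on the figure. A count over enrolled subjects, read beside listings and the accountability report, lets a reader see every loss. This stands as a reason to keep the crude count and to rate the matter as modest. It does not correct the percentage, which is the stated result.

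Losses may also be few. Section 5.3 requires willingness to attend, section 5.4 excludes subjects known to be at risk of loss, and sections 6.1 and 6.1.3 call for retention efforts. That is fair, and is why the table starts at 0.5% a year, where the effect is negligible.

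The later SAP may settle the matter. It may; its content is unknown, and one cannot assume that it will repeat or repair the rule. But section 8.3.2 states a specific rule rather than leaving a gap, so correcting it now is reasonable.

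A reader might infer that revision will be analysed on PP and so overstated. The documents do not support that: the specific wording in 8.3.2 points to a full set, *major* violation is undefined, and nothing says lost subjects are dropped. The PP reading shows only why the set must be named. In addition, events leading to revision are collected as SADEs (7.1.7) and tabulated under 8.3.3, where no PP restriction is stated.

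**Conclusion.** The concern holds in a limited form. The denominator is undefined, no rule covers incomplete follow-up, and with all enrolled as denominator the percentage understates the risk of revision. At an assumed revision rate of 2% a year and loss of 0.5 to 6% a year, the 10-year shortfall is about 0.1 to 1.1 subjects of 26. This rests on constant hazards and on loss unrelated to revision.

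A reader might infer that the study's safety conclusion is materially distorted. The documents do not support that: they give no rates, the shortfall is within sampling error throughout the table, and the primary endpoints are metal ions and imaging. The case for change is that the error is systematic, runs in the unhelpful direction for the question behind the study, and is cheap to remove.

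**What to change.** 1. In section 8.3.2, replace *full analysis set* with the ITT population (all enrolled), and state that the PP rule does not apply to revision.
2. Keep the crude count x/N. Add the cumulative incidence of revision from the baseline visit with a 95% CI, with death as a competing event.
3. Censor loss and withdrawal at the last date on which implant status is known from any contact: visit, telephone or record. Apply the same ascertainment date to events and non-events. Censoring losses at their last 3-yearly visit while counting revisions up to the loss itself biases the estimate upwards; in simulation with revision at 2% a year and loss at 2 to 6%, by roughly half to one and a half percentage points at 10 years.
4. Show the curve to end of study with numbers at risk, and quote a stated time point such as 10 years after baseline. Label it as conditional on implants unrevised at entry, about 8 to 9 years post implant. State that censoring assumes loss is unrelated to revision.
5. Do not count losses of unknown reason as revised. Section 6.1.2 allows withdrawal without a reason, so such a rule could approach the worst case, and it is imputation. If bounds are wanted, show a best and worst case labelled as bounds (in the count example, 3/26 = 11.5% and 9/26 = 34.6%) and reconcile this with the no-imputation statement in 8.5.
6. Use one numerator wording in the synopsis, 3.2 and 8.3.2.

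The cost is protocol and SAP wording and a standard SAS procedure. Operative date, implant status at visits and revision date are already collected; date of death is not named as an item and should be confirmed as recorded. The downside is wide intervals and a possibly less favourable figure.

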3.0 Study Design

This is a single arm, consecutive series study to collect relevant clinical, laboratory and radiological data in up to 26 subjects, who have been implanted with the SMF Short Modular Femoral Stem THA system at 1 site in Australia.

The Baseline visit will be determined as the first visit to site after Ethics approval for the study has been received. This will be approximately 8-9 years post implant. Enrolled subjects will be followed up to 20 years post SMF implant. The Baseline visit assessments are described in Section 5.5 and 5.6. Post Baseline, the study will allow for metal ion assessments every 3 years for asymptomatic subjects and annual assessments for subjects with pain, swelling, and/or functional limitations if assessed by the Principal Investigator to be related to the SMF implant, having ruled out all other probable causes for the subject. If the subject has elevated whole blood cobalt or chromium (defined as >7ppb) a MARS MRI or CT will be obtained. These types of imaging techniques are aimed at

detecting inflammatory degenerative evolution of periarticular soft tissues including pseudo-tumors. A functional Questionnaire, HOOS JR Questionnaire will be completed at all patient site visits.

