8.4 Hypothesis and Sample Size Calculation

The sample size was chosen based on the feasibility of recruitment only without regard for statistical power as this is a descriptive study to establish efficacy and safety data based on the selected primary outcomes. There is no available previous data or data from similar studies for sample size justification.

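### HOOS JR and the primary outcomes are given an efficacy purpose that a single-arm study starting 8-9 years after implantation cannot serve

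*Combined protocol and SAP*

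**What the plan says.** **Purpose.** Sections 3.2 and 8.3.2 both say of HOOS JR: "The score will be calculated to assess clinical efficacy". Section 8.3, titled as an efficacy analysis, adds: "The indicators of efficacy of hip arthroplasty with the SMF Short modular femoral stem will be evaluated through the analysis of primary and secondary endpoints". Section 8.4 says that "this is a descriptive study to establish efficacy and safety data based on the selected primary outcomes". Section 3.1 defines those primary outcomes as whole-blood cobalt and chromium, with MARS MRI or CT when either exceeds 7 ppb.

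**Timing.** Section 3.0 states: "The Baseline visit will be determined as the first visit to site after Ethics approval for the study has been received". It continues: "This will be approximately 8-9 years post implant". On the end point it says: "Enrolled subjects will be followed up to 20 years post SMF implant". HOOS JR is completed at study visits. Neither the Baseline list in section 5.5.1 nor Table 1 includes a pre-operative or retrospectively obtained score.

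**Analysis.** Section 8.3.2 plans descriptive summaries of the score at every recorded time point, covering every subject, and then: "An exploratory t-test will be fitted to evaluate the difference between baseline and end of study scores". It does not say whether the test is paired or what counts as the end-of-study score.

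**Who contributes.** Section 5.3 admits only patients whose implant is still in place at ethics approval. Section 6.1.7 ends follow-up at revision. Section 8.5 plans no imputation. Section 8.1 assigns every efficacy analysis to the per-protocol (PP) set.

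**The concern.** To show that a hip replacement works, one needs a score from before the operation, a comparison group, or at least an external value to compare with. The plan has none of these. Its only formal HOOS JR comparison begins long after any benefit of surgery would have appeared. It therefore addresses a different question: how reported hip function changes late in the life of the implant, among people who still have it.

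Three things are at stake.

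- **Interpretation.** A stable mean could be presented as evidence of efficacy, and a decline as evidence against it. Neither would follow.
- **Selection.** Section 1.0 says the sponsor considers that patients with modular necks may be at greater risk of revision. Exit by revision is therefore plausibly linked to function, and those who leave are likely to differ from those who stay.
- **Analysis set.** Because section 8.1 ties efficacy to the PP set, the label decides whose scores are counted.

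**Working it through.** There is no sample-size calculation to reproduce. Sections 8.0 and 8.4 set up to 26 subjects on feasibility alone, with no effect size, SD or power. The check rests on the timeline, the selection rules and the analysis sets.

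**1. Span of the comparison.** Baseline is at about year 8-9 and the end-of-study visit at year 20.
- 20 − 8 = 12 years; 20 − 9 = 11 years. This agrees with the synopsis, which gives a study length of about twelve years.
- Share of the 20 years before Baseline: 8/20 = 40%; 9/20 = 45%. The whole change from before to after surgery lies in that unobserved part, for every subject.

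**2. Possible contrasts.**
- Before against after surgery: not available, as no pre-operative score is collected.
- Against another implant or no implant: not available, as there is one arm.
- Against an external value: none is named.
- Late within-subject change: available, and this is what the t-test addresses.
- Metal ions and MARS MRI/CT, to which section 8.4 attaches efficacy: section 3.1 presents these as safety assessments.

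**3. Selection.** It acts at entry, because hips revised before ethics approval are excluded (5.3). It acts again during follow-up, because revised subjects leave (6.1.7). For them section 6.1.7 lists the revision date, adverse events and any available radiographs, with no mention of HOOS JR.

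**4. The end-of-study score.** Table 1 has a 20-year visit, but it also allows the end-of-study entry at Baseline, interim and unscheduled visits where applicable, and HOOS JR is marked at all of these. Read one way, the test uses only subjects seen at year 20. Read the other way, it mixes 11-12-year changes with shorter ones that end at early exit. The text does not choose.

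**5. Analysis set.** Section 8.1 with the efficacy label gives the PP set. Section 8.3.2 summarises HOOS JR in everyone. Section 13.0 counts missed data and out-of-window visits as deviations, and section 8.1 excludes major violations without saying what makes one major. The two sets could differ.

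**6. Illustrations under assumptions that are not in the documents.**
- Number with a year-20 score, 26 × (1 − a)^t, for combined annual loss a and t = 11 / 12 years:
  - a = 2%: 20.8 / 20.4
  - a = 3%: 18.6 / 18.0
  - a = 5%: 14.8 / 14.0
- Shift in the mean change if the worst fraction f of changes is lost. For a normal distribution this is φ(z_f)/(1 − f) in SD units, where z_f is the f-quantile:
  - f = 10%: 0.195
  - f = 20%: 0.350
  - f = 30%: 0.497
- If leaving correlates only 0.5 with change, the shifts halve to about 0.10, 0.18 and 0.25 SD. All are in the favourable direction.

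**The case against.** The best defence is that this is a descriptive safety study. Its objective is safety throughout, and section 8.3 itself opens by restating that objective. Section 8.2.1 calls all tests exploratory and unpowered. The t-test sentence says only that it will "evaluate the difference between baseline and end of study scores", and for late change those are sensible time points. Summaries at all recorded time points are already planned with confidence intervals, section 8.5 promises full accountability for death, revision, withdrawal and loss, and a more detailed SAP is to follow before database lock (8.2). The timing of Baseline is openly stated.

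Most of this stands, and it limits how far the criticism goes. A reader might infer any of the following, but the documents do not support them:

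- *The plan concludes, or commits itself to claiming, efficacy.* It states a purpose. There is no efficacy hypothesis or success criterion.
- *The t-test is declared to be the proof of efficacy.* The efficacy wording is attached to the score, and the test is described separately.
- *Only subjects unrevised at year 20 enter the test.* Table 1 leaves this open. Only the selection at entry is certain.
- *Any HOOS JR result is bound to be misread.* That is a prediction about readers. The text supports only that it could be.

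The defence does not remove the mismatch. Calling a test exploratory limits the strength of the inference; it does not turn late change in people already treated into an estimate of what the operation achieved. Nor does it resolve the conflict over the analysis set.

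**Conclusion.** The point holds as a mismatch between stated purpose and design. Efficacy, whether read from HOOS JR or from the primary outcomes, cannot be estimated here, because the design contains no contrast that would identify it. The t-test estimates about 11-12 years of late change in hips unrevised at entry, or fewer years for some subjects if early-exit scores are used. It cannot separate device performance from ageing or selective loss. The label also creates a conflict between sections 8.1 and 8.3.2 over whose scores are analysed.

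The timeline, the missing comparator and pre-operative score, and the conflict over sets come directly from the protocol. The retained counts (about 14-21 of at most 26) and the shifts in SD units rest on assumed loss. They show what selective loss could do and do not measure the error. The importance is moderate. HOOS JR is secondary, the primary safety data are unaffected, and the visit-by-visit summaries remain useful description. The wording should nevertheless be corrected before the detailed SAP is finalised, because it governs what may be concluded and in which subjects.

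**What to change.** - Remove the efficacy purpose from sections 3.2, 8.3, 8.3.2 and 8.4.
- Define the HOOS JR endpoint as patient-reported hip function from about 8-9 to 20 years after implantation, in subjects unrevised at entry. Analyse it in all enrolled subjects and describe it by years since implantation. Show symptomatic and non-symptomatic subjects separately, since the former are seen annually and the latter every three years; otherwise the years between three-yearly visits would represent mainly symptomatic subjects.
- Specify the Baseline-to-end comparison as a paired within-subject change. State which score counts as the end-of-study score and whether early-exit scores qualify. State that no efficacy inference will be drawn.
- Tabulate the Baseline and last available scores of subjects who died, were revised or left beside those of subjects who reached the 20-year visit.

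The cost is wording in the protocol and SAP and one extra table, with no new visits or data. The sponsor gives up an efficacy statement that the data could not have supported.

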8.2.1 General

The subjects will be described and summarised using the collected baseline demographic and medical variables which include but are not limited to age, gender, ethnicity, medical and medication history, diagnostic factors.

Primary and secondary endpoints will be evaluated using listings and appropriate summary statistics. The summary statistics for both primary and secondary outcomes will be reported together with a 95% confidence interval to assess the degree of precision in the estimates.

Summary statistics for baseline data, primary and secondary endpoints will be given according to the nature of the variable, continuous or categorical. For categorical variables, the number of observations, mean, standard deviation, median, minimum, and maximum will be presented, while for categorical variables the number of observations, frequency, and percentages will be reported.

All statistical tests will be exploratory in nature as the study is not powered for any statistical testing. Appropriate parametric and/or non-parametric analyses will be chosen for statistical analysis. Test of association for the table of counts will be based on the Fisher's Exact Test unless otherwise inappropriate. The exploratory analysis of continuous variables will be done using t-test if appropriate. The Wilcoxon rank-sum test will be explored if the data is non-normal. All statistical tests will be considered at 5% significance level.

All statistical analyses and calculation of confidence intervals will be performed using SAS software.

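### The only fallback named for non-normal data, Wilcoxon rank-sum, does not suit the within-subject HOOS JR comparison, and no paired test is named (minor)

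*Combined protocol and SAP*

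**What the plan says.** Section 3.0 describes the design: "This is a single arm, consecutive series study to collect relevant clinical, laboratory and radiological data in up to 26 subjects". It adds: "A functional Questionnaire, HOOS JR Questionnaire will be completed at all patient site visits". The schedule in Table 1 (section 5.6) includes HOOS JR at both the Baseline and the EOS visit.

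Section 8.3.2 plans one test for this endpoint: "An exploratory t-test will be fitted to evaluate the difference between baseline and end of study scores". It does not say whether the t-test is paired and gives no alternative for non-normal scores. This is the only t-test that the document ties to a named endpoint.

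Section 8.2.1 gives the general rule for continuous variables: "The exploratory analysis of continuous variables will be done using t-test if appropriate", followed by "The Wilcoxon rank-sum test will be explored if the data is non-normal". It does not say which quantity is to be judged non-normal or how. The same paragraph also says: "Appropriate parametric and/or non-parametric analyses will be chosen for statistical analysis". It calls all tests exploratory and sets the 5% level.

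Section 8.2 leaves detail to a later document: "The SAP will be more detailed and account for all analyses". Section 8.3 adds: "For all continuous endpoints, 95% confidence intervals (CI) for the means will be reported". No signed-rank, sign or other paired test is named anywhere.

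**The concern.** Baseline and end-of-study HOOS JR scores come from the same subjects. The t-test in 8.3.2 is most naturally read as paired. The one non-parametric alternative on the page is the rank-sum test, which treats its two samples as unrelated. An analyst who finds non-normal HOOS JR scores and follows 8.2.1 literally would move from a paired test to an unpaired one and discard the within-subject pairing.

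If scores within a subject are positively correlated, that makes a real change in function more likely to be reported as no clear change. In a safety follow-up of a device removed from the market, that is the less welcome direction of error. Pairs are also few: at most 26 subjects, revised subjects leave follow-up (6.1.7), and missing data are not imputed (8.5).

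**Working it through.** **No figure to reproduce.** The sample size of up to 26 is based on feasibility (8.0, 8.4). The document gives no SD, effect size, correlation or power for HOOS JR. Every input below except the 26 and the 5% level is an assumption.

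**Step 1: why an unpaired test is conservative here.** With common SD σ, correlation ρ and n pairs, the variance of the mean difference is 2σ²(1 − ρ)/n. An unpaired test acts as if it were 2σ²/n. Its large-sample two-sided type I error is therefore 2 × [1 − Φ(1.96/√(1 − ρ))]:

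- ρ = 0: 1.96/1 = 1.96, giving 0.050
- ρ = 0.3: 1.96/0.837 = 2.34, giving 0.019
- ρ = 0.5: 1.96/0.707 = 2.77, giving 0.006
- ρ = 0.7: 1.96/0.548 = 3.58, giving 0.0003

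The error rate falls below 5% as ρ rises and does not exceed it for ρ ≥ 0.

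**Step 2: test against test, simulated.** Assumptions: 26 pairs, two-sided 5%, and a 0–100 scale on which a lower score is worse. Scores are latent bivariate normal with mean 90 and SD 18, then rounded and capped. The latent decline is 0 (type I error) or 12 (power). After capping, the baseline SD is about 14 and the mean decline about 9.7. There were 10,000 trials per setting, so the Monte Carlo standard error is at most 0.5 points.

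| ρ | 0 | 0.3 | 0.5 | 0.7 |
|---|---|---|---|---|
| Type I error, rank-sum (%) | 4.2 | 2.4 | 0.7 | 0.2 |
| Type I error, signed-rank (%) | 4.7 | 5.3 | 4.8 | 4.5 |
| Power, rank-sum (%) | 61 | 64 | 65 | 69 |
| Power, signed-rank (%) | 59 | 74 | 86 | 97 |

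At zero correlation nothing is lost.

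**Step 3: the whole rule.** The plan names no normality check, so Shapiro-Wilk at 5% is assumed. The rule as written is paired t, or rank-sum if the check fails. The corrected rule checks the differences and uses signed-rank if they fail. Values are for ρ = 0.3/0.5/0.7 with 26 pairs.

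| Latent mean/SD, latent decline | Quantity checked | Fallback used (%) | Power as written (%) | Power corrected (%) | Loss (points) |
|---|---|---|---|---|---|
| 90/18, 12 (strong ceiling) | raw scores | 95/94/94 | 64.7/67.0/70.7 | 75.4/86.2/97.3 | 10.7/19.2/26.6 |
| 90/18, 12 | differences | 6/8/13 | 74.5/84.2/92.7 | 75.4/86.2/97.3 | 0.9/2.0/4.6 |
| 85/15, 7.5 (moderate ceiling) | raw scores | about 53 | – | – | about 6/16/28 |
| 75/15, 7.5 (weak ceiling) | raw scores | about 10 | – | – | about 1/3/5 |

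The last two rows come from smaller runs (2,000 trials per setting). Loss is corrected power minus power as written, for example 75.4 − 64.7 = 10.7. Across repeat runs, checking the differences or having a weak ceiling puts the loss at about 1–2/2–3/3–5 points.

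**Step 4: paired t-test with no fallback.** In the strong-ceiling scenario its power is about 75/86–87/98%, level with the corrected rule, and its type I error is about 5%.

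**Step 5: fewer pairs.** With 18 pairs and a strong ceiling, the raw-score check gives 48.0/50.4/54.6% against 57.1/70.5/89.0% corrected, a loss of 9.1/20.1/34.4 points. Checking the differences gives 56.2/68.4/83.6%, a loss of 0.9/2.1/5.4 points.

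**The case against.** The strongest reply is that the text does not commit the error. Section 8.3.2 names a t-test for HOOS JR and nothing else. Section 8.2.1 is general, does not mention HOOS JR, promises appropriate analyses, and says that rank-sum will be explored, not that it replaces a test named for an endpoint. Rank-sum also has a proper use in this study, because 8.3.1 and 8.3.2 break results down by symptoms, which compares different subjects. Section 8.2 calls its content brief and defers detail to a SAP to be finalized before database lock.

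The large losses also need several assumptions together: a normality gate, applied to raw scores although the t-test is paired, and a marked ceiling. As the ceiling weakens, that gate triggers the fallback in about 94%, 53% or 10% of trials. A paired t-test used alone needs no rescue.

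All of this stands, and it limits the point to a conditional one of small size. It does not remove the point. The permissive sentences allow a paired test without naming one, and the one fallback that is named does not fit the one comparison to which the document ties a t-test. Which quantity is checked for normality is also unstated, and the table shows that this choice separates a trivial loss from a large one.

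**Conclusion.** The point holds conditionally and is minor. If the general rule in 8.2.1 is applied to the HOOS JR comparison, it puts an independent-samples test on paired scores. For 26 pairs and correlations of 0.3/0.5/0.7, the cost in power is about 1–2/2–3/3–5 points if the differences are checked or the ceiling is weak. It is about 11/19/27 points if raw scores with a strong ceiling are checked. The distribution, decline, correlation and normality check are all assumed, so these figures show a range and do not predict the result.

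A reader might infer three stronger things, and the documents support none of them:

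- *That the plan prescribes rank-sum for HOOS JR.* It does not link the two, and it leaves room for an appropriate test.
- *That a loss of 11 to 27 points is to be expected.* That is the upper part of the range and depends on a check that the plan does not specify.
- *That false positives are inflated.* With positive correlation the error runs the other way.

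The test is exploratory, the endpoint is secondary and the study is not powered for testing. Visit-level summaries and confidence intervals are reported whatever the p-value.

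**What to change.** In 8.3.2, specify a paired t-test on the within-subject change in HOOS JR, or the Wilcoxon signed-rank test if the differences are non-normal. In 8.2.1, limit the rank-sum test to comparisons between different subjects, such as symptom subgroups. Carry both statements into the SAP before database lock.

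An optional addition is to report the mean change with its 95% confidence interval and the number of complete pairs. The intervals promised in 8.3 are for means and do not mention the change.

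The cost is a few words in two sections and the SAP. No new data are needed and no visit changes.
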